8.5 Other Drugs/Therapies

Drugs or therapies previously used before procedure in the treatment of the primary disease should be discontinued as a general rule, unless they are used also for pre-procedural complication. Drugs or therapies used before procedure in the treatment of pre-procedural complication should be maintained as much as possible. This does not apply to the cases where it is used for an AE or aggravated primary disease.

<Rationales for the setting>

Since treatments of the primary disease may affect the evaluation of this clinical trial, the use of these drugs or therapies should be discontinued as a general rule. If the same treatment is maintained from prior to the procedure, other treatments of complication may not affect the evaluation of this clinical trial, considering well-being of the trial subjects, these could be concomitantly used.

8.6 Precautions for Concomitant Drugs/Concomitant Therapy and Input Procedure in Electronic Case Report Forms

8.6.1 Anticoagulant/antiplatelet drugs and antibiotics

Observe anticoagulant/antiplatelet drug (excluding anticoagulant at dialysis) from 7 days prior to the day of

- Vasoconstrictor
- Vasodilator
 - Coronary vasodilator
 - Peripheral vasodilator
- Hyperlipidemia agent
 - HMG-CoA reductase inhibitor (statin)

9 STUDY ENDPOINTS

9.1 Primary Endpoints

- Mortality at 1 year post-procedure

<Rationales for the setting>

Based on the fact that the study device EWJ-003 is clinically positioned as a device that enables us to treat chronic dialysis AS patients who have not been eligible for SAVR and have not had any radical treatments so far, it is important to evaluate whether or not improvement in the prognosis, the goal of the therapy, could be achieved for evaluation of the safety and efficacy of EWJ-003. Since the Valve Academic Research Consortium (VARC) guidelines recommend that the mortality at 1 year post-procedure be set for the primary endpoint in clinical trials,^[55] the mortality at 1 year post-procedure was set up for the primary endpoint for this clinical trial.

9.2 Secondary Endpoints

9.2.1 Secondary safety endpoints

- Composite endpoint: Post-procedure 30 days, 6 months, 1 year, and 2 to 5 years annually
 - Death and stroke
- Single endpoints: Post-procedure 30 days, 6 months, 1 year, and 2 to 5 years annually
 - Death (cardiovascular, non-cardiovascular)
 - MI (periprocedural, spontaneous)
 - Stroke (disabling, non-disabling)
 - Bleeding (life-threatening or disabling, severe, mild)
 - Vascular access site/access-related complications
 - Severe vascular complications
 - Conduction disorder/arrhythmia
 - Conduction disorder requiring new pacemaker implantation
 - Aortic valve re-intervention
 - Coronary obstruction
 - Endocarditis
 - Valve explants
 - Structural valve deterioration
 - Nonstructural valve dysfunction

Table 10-1: Permissible time windows for the tests/observations

Test/observation timing	Baseline ^{a)}	Procedure ^{b)}	Immediately after procedure	Post-procedural follow-up observation		
				Hospital discharge	30 days post-procedure	6 months post-procedure
Reference date (time)	-	Day 0	Up to 72 hours after exiting the operation room	7 days post-procedure or hospital discharge, whichever comes earlier	30 days post-procedure	182 days post-procedure
Permissible time window	Within 60 days pre-procedure	-	-	± 2 days	-7 days/+14 days	± 30 days

^{a)} The 12-lead ECG should be performed within 48 hours prior to entering the operation room, clinical laboratory tests within 14 days prior to the procedure, and coronary angiography and aortofemoral blood vessel evaluation (CT, MRI, or X-ray) within 90 days pre-procedure (see Section 10.2.1 "Baseline"). For the continued access registry, except cases that may be clinically valid, coronary angiography should be performed within 1 year prior to the study procedure.

^{b)} Cardiac catheter test at procedure should be performed immediately before and after the procedure.

Table 10-2: Permissible time windows for the tests/observations

Test/observation timing	Post-procedural follow-up observation				
	1 year post-procedure	2 years post-procedure	3 years post-procedure	4 years post-procedure	5 years post-procedure
Reference date	365 days post-procedure	730 days post-procedure	1095 days post-procedure	1460 days post-procedure	1825 days post-procedure
Permissible time window	± 30 days	± 45 days	± 45 days	± 45 days	± 45 days

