	
Secondary Endpoints
 
<Secondary Safety Endpoints>
 
 • Composite endpoint: 30 days, 6 months, 1 year, and 2 to 5 years annually 
 ◦ Death and stroke • Single endpoints: 30 days, 6 months, 1 year, and 2 to 5 years annually 
 ◦ Death (cardiovascular, non-cardiovascular) ◦ MI (periprocedural, spontaneous) ◦ Stroke (disabling, non-disabling) ◦ Bleeding (life-threatening or disabling, major, minor) ◦ Vascular access site/access-related complications ◦ Major vascular complications ◦ Conduction disturbance/arrhythmia ◦ Conduction disturbance requiring new pacemaker implantation ◦ Aortic valve re-intervention ◦ Coronary obstruction ◦ Endocarditis ◦ Valve explants ◦ Structural valve deterioration ◦ Nonstructural valve dysfunction 
<Secondary Efficacy Endpoints>
 
 • Device success: 30 days • Length of hospitalization /ICU stay: Discharge • NYHA Classification: 30 days, 6 months, 1 year, and 2 to 5 years annually • Six-minute walk test: 30 days and 1 year • Quality of Life (QOL): 30 days, 6 months, 1 year, and 2 to 5 years annually 
<Secondary Valve Performance Endpoints>
 
 • Echocardiography: 30 days, 6 months, 1 year, and 2 to 5 years annually 
 ◦ Mean pressure gradient ◦ Peak gradient ◦ Effective orifice area (EOA) ◦ Effective orifice area index (EOAi) ◦ Aortic valve regurgitation (paravalvular, transvalvular) ◦ Left Ventricular Ejection Fraction (LVEF)

Item	Content																			
	
 Left ventricular mass Left ventricular mass index (LVMI) 																			
Target Sample Size	
A total of 30 subjects
 
 At least 2 subjects for each approach (TF, TA, and TAo) should be enrolled. At least 1 subject each for THV sizes. Enrollment will be closed when the number of patients enrolled in the study reaches the target sample size even when the above-mentioned number of patients are not ensured. Additional subjects will not be included for discontinued subjects. 																			

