10.2.8 Years 2 through 5 annual post-procedure visits

The tests/observation at 2 to 5 years post-procedural follow-up should be performed within the permissible time windows shown in Section 10.1 “Test/observation schedule” to collect the data on the following items.

- NYHA classification of cardiac performance (see Section 30 “GLOSSARY”)
- CCS status of stable angina (see Section 30 “GLOSSARY”)
- Echocardiography
 - Perform echocardiography in reference to the Echo Core Laboratory Procedure to measure/evaluate the following items. The resulted echocardiographic images should be

- 84 -

- submitted to the Echo Core Laboratory.
- [Measurements/endpoints]
 - Cardiac output, aortic valve pressure gradient (mean/maximum), EOA, EOA_i¹, aortic valve regurgitation (severity/regurgitation site), maximum blood flow rate, LVEF, left ventricular mass, LVMI¹
 - * Baseline values must be used for calculation of EOA_i and LVMI.
- QOL questionnaire
 - EuroQOL (see Appendix 4)
 - SF-12 (Appendix 5)
- Anticoagulant/antiplatelet drugs
- AE/device deficiency

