CCS status of stable angina	
Class 1: No limits to physical activities. Ordinary physical activity does not cause angina, such as walking and climbing stairs. Angina with strenuous or rapid or prolonged exertion at work or recreation.
 
Class 2: Slight limitation of ordinary activity. Angina with walking or climbing stairs rapidly, walking uphill, walking or stair climbing after meals, or in cold, or in wind, or under emotional stress, or only during the 1 to 2 hours after awakening. Or walking more than two blocks on the level and climbing more than two flight of ordinary stairs at a normal pace and in normal conditions.
 
Class 3: Marked limitation of ordinary activity. Angina with walking one or two blocks (80 m - 160 m) on the level and climbing one flight of stairs in normal conditions and at normal pace.
 
Class 4: Inability to carry on any physical activity without discomfort. Anginal symptoms may be present at rest.
	CCS
Cancer	Refers to a condition caused by an uncontrolled division of abnormal cells conditions, and is characterized by invasion into the surrounding tissues, and can progress to distant metastasis. Cancer is classified into benign and malignant, and in this clinical trial, if a subject has a history of malignant cancer, enter as a subject with a history of cancer at baseline in the eCRF.	
Cardiac tamponade	Newly occurred pericardial effusion associated with hemodynamic instability and a clear causal relationship to the study procedure.	VARC-2
Conduction disorder/arrhythmia	
The following data on conduction disorder/arrhythmia will be collected:
 
 Conduction disorder at baseline, paroxysmal or persistent atrial fibrillation/flutter, and permanent pacemaker implantation New or aggravated conduction disorder related to the implanted valve 	VARC-2

Term	Definition	Reference/rationale

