	
 First degree atrioventricular (A-V) block Second degree A-V block (Mobitz type I or II) Third degree A-V block Incomplete right bundle branch block Right bundle branch block Defect intraventricular conduction Left bundle branch block Left anterior hemiblock (LAH) Left posterior hemiblock (LPH) Block requiring permanent pacemaker implantation Persistent or transient advanced A-V block 
When advanced A-V block is observed at every test, it is regarded as persistent.
 
 New permanent pacemaker implantation 
The indications of permanent pacemaker implantation and the number of days after the procedure should be accurately recorded.
 
 Newly found atrial fibrillation/flutter Newly found arrhythmia with hemodynamic instability or requiring treatments 	
Switching to surgery	Refers to cases with switching to open heart surgery by sternotomy due to a procedure-related complication during the study procedure.	VARC-2
Coronary obstruction	During the study procedure or post-procedure newly found prosthetic valve, native cusp, lump lime, or partial or total occlusion at the coronary ostium associated with dissociation in the angiogram or echocardiography findings.	VARC-2
Death	
Death is classified into cardiovascular death or non-cardiovascular death by the cause of death.
 
 Cardiovascular death 
 When applicable to the followings, it is regarded as cardiovascular death: 
 Death directly associated with the heart (e.g.: myocardial infarction, cardiac tamponade, worsened heart failure) Death associated with blood vessels other than the coronary artery (e.g.: neurological event, pulmonary embolism, aortic aneurysm rupture, dissecting aneurysm, and other vascular disease) All study procedure-related deaths, including deaths related to procedural complication and treatments for the procedural complication. All deaths related to the investigational valve, including deaths from structural valve deterioration, non-structural dysfunction, and other valve-related AEs. Sudden death and unwitnessed death Death with unknown cause Non-cardiovascular death 
 It is apparent that the major cause of death is a disease other than the above (e.g.: trauma, cancer, suicide) 	VARC-2

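### Conduction disorder/arrhythmia is reported annually to year 5, but the last scheduled ECG is at 1 year, so year 2-5 figures for ECG-read items are likely biased low

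*Combined protocol and SAP*

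**What the plan says.** **Endpoint and timing.** Section 9.2.1 gives a single timetable for all single safety endpoints: "Single endpoints: Post-procedure 30 days, 6 months, 1 year, and 2 to 5 years annually". The list beneath it includes "Conduction disorder/arrhythmia". The synopsis names the same endpoint "Conduction disturbance/arrhythmia", with the same time points.

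**Definition.** Section 30 (Glossary) lists what is collected. One heading is "New or aggravated conduction disorder related to the implanted valve". The items itemised there begin with "First degree atrioventricular (A-V) block" and go on to higher-degree blocks, complete and incomplete bundle branch block and the left hemiblocks. The entry also covers new permanent pacemaker implantation, new atrial fibrillation or flutter, and "Newly found arrhythmia with hemodynamic instability or requiring treatments".

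**Schedule.** Sections 10.2.3 to 10.2.7 list a 12-lead ECG immediately after the procedure, at discharge, at 30 days, at 6 months and at 1 year. Section 10.2.8 opens: "The tests/observation at 2 to 5 years post-procedural follow-up should be performed within the permissible time windows". It then lists NYHA class, CCS class, echocardiography, quality of life, anticoagulant/antiplatelet drugs and adverse events or device deficiencies. It lists no ECG.

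**Analysis.** Section 15.1.2 treats secondary endpoints descriptively, without tests, and allows Kaplan-Meier cumulative incidence for the secondary safety endpoints where needed.

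**The concern.** A first-degree block, a hemiblock or a silent episode of atrial fibrillation is unlikely to be noticed unless someone records an ECG. Up to 1 year the plan records one at set visits. From year 2 it does not, yet the endpoint keeps its name and its annual reporting. Nothing in Section 9.2.1, the synopsis or Section 15.1.2 says that the way events are found has changed.

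Section 1.1.3 gives confirmation of long-term safety and efficacy as a reason for the 5-year follow-up. A table or curve in which new conduction events become rarer after year 1 could be taken as reassurance on long-term safety, when part of the slowing comes from the visit schedule.

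**Working it through.** The plan gives no rate or sample size for this endpoint, so there is no figure to reproduce. The check compares the endpoint timetable with the visit lists.

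| Endpoint time point (9.2.1) | 12-lead ECG scheduled | Source |
|---|---|---|
| 30 days | yes | 10.2.5 |
| 6 months | yes | 10.2.6 |
| 1 year | yes | 10.2.7 |
| 2, 3, 4 and 5 years | no | 10.2.8 |

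The ECGs immediately after the procedure (10.2.3) and at discharge (10.2.4) bring the post-procedure total to five, all within the first year. Time points without a scheduled ECG: 4 of 7. In Table 10-3 the ECG row stops one column before the NYHA row, which does run to years 2-5. That agrees with Section 10.2.8. Section 10.3.8 shows the same gap for the continued access registry.

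**Comparison with other endpoints.** The six-minute walk is an endpoint at 30 days and 1 year only (9.2.2), and those are the visits at which it is done (10.2.5, 10.2.7). The echocardiographic endpoints run to year 5 (9.2.3), with echocardiography at each annual visit (10.2.8). For conduction disorder, the shared timetable extends past the test.

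**What still reaches the data after 1 year.** Section 11.1 keeps adverse event observation open to the final visit, and Section 10.2.8 collects adverse events annually. Section 11.3 lets a clinically important finding from a test outside the protocol be handled as an adverse event if it is serious or the investigator judges it to be one. So an ECG done in routine care can supply an event, but it has to be done, noticed, judged important and reported.

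**Illustration (assumed values, none from the documents).** Let c be the 1-year cumulative incidence, r the true annual risk of a first ECG-only event in years 2-5, and f the share captured through adverse event reporting. Ignoring death, the reported 5-year incidence is

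1 − (1 − c)(1 − r·f)^4.

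For c = 20%:

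| r | f = 0% | f = 25% | f = 50% | f = 100% |
|---|---|---|---|---|
| 2% | 20.0% | 21.6% | 23.2% | 26.2% |
| 5% | 20.0% | 23.9% | 27.7% | 34.8% |
| 10% | 20.0% | 27.7% | 34.8% | 47.5% |

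Worked cell, r = 5% and f = 25%: 1 − 0.80 × (1 − 0.0125)^4 = 1 − 0.80 × 0.9509 = 23.9%. With full capture it is 1 − 0.80 × 0.95^4 = 34.8%.

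For c = 40%, the same r and f give 42.9% against 51.1%. The curve is flat only when f = 0. With partial capture it rises, but too little.

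**The case against.** The strongest reply is that late follow-up in this trial rests on adverse event reporting by design. Head CT, NIHSS and cardiac enzymes also stop after 1 year, while stroke and MI remain annual endpoints. Adverse events are collected to the final visit, and Section 11.3 admits findings from unscheduled tests. New pacemaker implantation and unstable or treated arrhythmia need no scheduled ECG. The itemised blocks count only if new or aggravated and related to the implanted valve, which narrows what could be missed. The endpoint is untested, Kaplan-Meier is optional, and the report for the approval application uses 1-year data (Section 18.3).

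Most of this stands, and it limits the point. A reader might infer that ECG-only events cannot be seen after year 1, that the later curve must be flat, or that the year 2-5 figures have no measurement behind them. The adverse event route rules out all three. Nor should the glossary sentence "When advanced A-V block is observed at every test, it is regarded as persistent" be read as defining the endpoint by repeated ECG, since it only separates persistent from transient advanced block.

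The reply does not close the gap. By the glossary a stroke begins with an acute neurological deficit, so it tends to declare itself. A hemiblock or first-degree block does not. The valve-related qualifier does not attach to new atrial fibrillation. Opportunistic reporting is a weaker method than a scheduled ECG, and the plan does not say that one replaces the other.

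**Conclusion.** The point holds in a limited form. After 1 year, events visible only on ECG are found opportunistically, so the year 2-5 figures for those items are likely too low and are not comparable with the first year. Four of seven time points are affected. The size of the bias cannot be derived from the documents; the illustration shows only how it depends on the assumed late risk and capture.

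The conclusion assumes that some silent qualifying events occur after year 1 and that routine care does not detect and report all of them. It rests on Section 10.2.8, with Table 10-3 in agreement. A reader might also infer that the synopsis Table I contradicts them, because its ECG row appears to carry a year 2-5 mark. In the text as extracted, that row has the same marks as the six-minute walk row, which cannot be right given Section 9.2.2. This is a reading artefact, and no error in Table I is claimed.

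The effect is confined to one descriptive secondary endpoint. The 1-year mortality endpoint and its test are untouched.

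**What to change.** In Section 9.2.1 and the synopsis, limit the ECG-read conduction and arrhythmia items to 30 days, 6 months and 1 year. For years 2-5, report new pacemaker implantation and AE-reported arrhythmia or conduction disorder on separate lines, labelled as ascertained from adverse event reports without a scheduled ECG. If a cumulative incidence curve is drawn for the full endpoint, end it at 1 year.

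The cost is endpoint wording and table shells, with no test added for subjects. The downside is that four annual figures for one descriptive endpoint are dropped or relabelled. A lighter alternative is to keep the timetable and footnote every year 2-5 figure with the change in ascertainment. That discloses the bias but leaves the two methods joined in one series.

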9.2.2 Secondary efficacy endpoints

- Device success: 30 days after procedure
- Length of post-procedural hospitalization/ICU stay: At discharge
- NYHA classification: Post-procedure 30 days, 6 months, 1 year, and 2 to 5 years annually
- Six-minute walk test: Post-procedure 30 days and 1 year
- Quality of life (QOL) (EuroQOL, short form 12-item health survey [SF-12]): Post-procedure 30 days, 6 months, 1 year, and 2 to 5 years annually

9.2.3 Secondary valve performance endpoints

- Echocardiography: Post-procedure 30 days, 6 months, 1 year, and 2 to 5 years annually
 - Mean pressure gradient
 - Peak gradient
 - EOA
 - EOAi
 - Aortic valve regurgitation (paravalvular, transvalvular)
 - LVEF
 - Left ventricular mass
 - Left ventricular mass index (LVMI)

10 TEST/OBSERVATION DATA COLLECTION

10.1 Test/Observation Schedule

All registered subjects in this clinical trial will receive the tests/observations shown in Section 10.2 "Test/observation items". Post-procedural follow-up observation will be performed at post-procedure 30 days, 6 months, 1 year, and 2 to 5 years annually.

The permissible time window for each test/observation period is as shown in Table 10-1 and Table 10-2, and the day of procedure is counted as Day 0. The time of the day of procedure is specified as between 0:00 and 23:59, and 24:00 should be expressed as 0:00. If the procedure spans before and after 0:00, the day when the procedure was started should be counted as date of procedure (initial day). The time of the start and end of the procedure is the time when invasion such as incision was made on the access site and the time when closing the access site such as incision site was completed, respectively.

The test/observation schedule is shown in Table 10-3. The test/observation schedule for the continued access registry is as shown in Table 10-4.

Table 10-3: Schedule of Tests and Observations

Tests/observations	Timing										
	Baseline (Within 60 days pre-procedure)	During procedure	Immediately after procedure (Within 72 hours post-procedure)	30 days post-procedure (± 2 days)	6 months post-procedure (± 30 days)	1 year post-procedure (± 30 days)	2-5 years post-procedure (± 45 days)	Discontinued	Unscheduled visit		
Informed consent	X										
Inclusion/exclusion criteria	X										
Patient background	X										
Surgical risk assessment ¹⁾	X										
NYHA classification of cardiac performance	X			X	X	X	X	X			
CCS status of stable angina	X			X	X	X	X	X			
Neurological assessment ²⁾ (NIHSS, mRS)	X				X	X	X				
Blood pressure	X			X	X	X	X				
12-lead ECG	X ³⁾		X	X	X	X	X				
Chest X-ray	X		X	X	X	X	X				
Head CT	X			X	X	X	X				
6-minute walk test	X			X	X	X	X				
Clinical laboratory test	Hematology	X ⁴⁾			X	X	X				
	Biochemistry	X ⁴⁾			X	X	X				
	Coagulation	X ⁴⁾			X	X	X				
	Cardiac enzyme	X ⁴⁾	X	X	X	X	X				
Echocardiography	X	X ⁵⁾		X ⁶⁾	X ⁷⁾	X ⁸⁾	X ⁹⁾	X ¹⁰⁾			
Cardiac CT	X										
Coronary angiography	X ⁹⁾										
Aortofemoral imaging	X ⁹⁾										
Cardiac catheterization	X ⁹⁾										
QOL questionnaire (EuroQOL, SF-12)	X				X	X	X	X			
Procedure information		X									
Anticoagulant/antiplatelet drugs	X ¹¹⁾					X					
Antibiotic	X ¹¹⁾		X								
Blood purification			X ¹⁰⁾				X				
Other concomitant medication/therapy					X					X ¹²⁾	X ¹²⁾
Adverse event/device deficiency							X				

¹⁾ Calculate STS score, Logistic EuroSCORE, and EuroSCORE II.
²⁾ For patient who has suffered a stroke, mRS must be evaluated within 30 to 90 days and beyond 90 days as earlier as from the onset of stroke.
³⁾ Perform within 48 hours prior to entering the operating room.
⁴⁾ Perform within 14 days prior to the study procedure.
⁵⁾ Perform within 90 days prior to the study procedure.
⁶⁾ Perform CT, MRI, or X-ray within 90 days prior to the study procedure.
⁷⁾ Start assessment from 7 days pre-procedure.
⁸⁾ Measure the aortic annulus diameter, and perform observation items of cardiac catheterization according to the situation.
⁹⁾ Perform pre- and post-study procedure. May be performed by echocardiography according to the situation.
¹⁰⁾ Assess dialysis information performed from the latest date prior to the study procedure to discharge (at discharge date or 7 days post-procedure, whichever came earlier).
¹¹⁾ Baseline BSA value must be used for calculation of EOAi and LVMI.
¹²⁾ Assess other concomitant medication/therapy, excluding anticoagulation/antiplatelet, antibiotic, and hemodialysis, within 1 year post-procedure.

Table 10-4: Schedule of Tests and Observations for Continued Access Registry

Tests/Observations	Timing	Timing													
		Baseline (Within 60 days pre-procedure)	During procedure	Immediately after procedure (Within 72 hours pre-procedure)	Discharge or 7 days post-procedure (± 2 days)	30 days post-procedure (± 7 days, ± 14 days)	6 months post-procedure (± 30 days)	1 year post-procedure (± 30 days)	2-5 years post-procedure (± 4-6 days)	Discontinued	Unscheduled visit				
Informed consent		X													
Inclusion/exclusion criteria for continued access registry		X													
Patient background		X													
Surgical risk assessment ¹¹		X													
NYHA classification of cardiac performance		X			X	X	X	X	X						
CCS status of stable angina		X			X	X	X	X	X	X					
Neurological assessment ¹² (NIHSS, mRS)		X				X	X ¹³	X ¹³							
Blood pressure		X			X	X	X	X							
12-lead ECG		X ¹⁴		X	X	X	X	X							
Chest X-ray		X		X	X	X	X	X							
Head CT		X			X	X ¹⁵	X ¹⁵								
Clinical laboratory test	Hematology	X ¹⁶				X	X	X							
	Biochemistry	X ¹⁷				X	X	X							
	Coagulation	X ¹⁸				X	X	X							
	Cardiac enzyme	X ¹⁹	X		X	X	X	X							
Echocardiography		X	X ²⁰		X ¹²	X ¹²	X ¹²	X ¹²	X ¹²						
Cardiac CT		X													
Coronary angiography		X ²¹													
Aortofemoral imaging		X ²²													
Cardiac catheterization			X ²³												
QOL questionnaire (EuroQOL-SF-12)		X				X ¹³	X ¹³	X ¹³	X ¹³						
Procedure information			X												
Anticoagulant/antiplatelet drugs		X ²⁴					X								
Blood purification				X ¹¹				X							
Other concomitant medication/therapy					X ¹⁴							X ¹⁴	X ¹⁴		
Adverse event/device deficiency							X								

¹¹ Calculate STS score, Logistic EuroSCORE, and EuroSCORE II.

¹² For patient who has suffered a stroke, mRS must be evaluated within 30 to 90 days and beyond 90 days as earlier as from the onset of stroke.

¹³ Subjects who developed stroke only.

¹⁴ Perform within 48 hours prior to entering the operating room.

¹⁵ Perform within 14 days prior to the study procedure.

¹⁶ Except cases that may be clinically valid, perform within 1 year prior to the study procedure.

¹⁷ Perform CT, MRI, or X-ray within 90 days prior to the study procedure.

¹⁸ Start assessment from 7 days pre-procedure.

¹⁹ Measure the aortic annulus diameter, and perform observation items of cardiac catheterization according to the situation.

²⁰ Perform pre- and post-study procedure. May be performed by echocardiography according to the situation.

²¹ Assess diabetes information performed from the latest date prior to the study procedure to discharge (at discharge date or 7 days post-procedure, whichever came earlier).

²² Baseline BSA value must be used for calculation of EOA¹ and LVMI.

²³ Subjects who were included in the continued access registry under Protocol ver. 5 will require no post-procedural QOL questionnaire.

²⁴ Where possible, assess other concomitant medication/therapy, excluding anticoagulation/antiplatelet, antibiotic, and hemodialysis, within 1 year post-procedure.

